Subjects who learn of the study through their physician or through advertisement and are interested will be asked to initiate contact with the study staff. Patients who respond to website advertising may elect to fill out a survey regarding eligibility that will ask them to provide contact information if they are willing to be contacted. Alternatively, if a patient's physician obtains the patient's permission for study staff contact, we may contact potential participants who have been identified as suitable by local providers. For patients seen clinically by the PI or other physician investigators involved in the study, the following procedures will be followed to ensure that subjects do not feel obligated to participate because of the involvement of their regular physician: The provider may mention the study to the patient and provide a flyer or consent form for the subject to take home. If this occurs, the provider will not talk further about the study unless the patient initiates the conversation by expressing interest. Alternatively, the patient's provider may mention the study and either ask the patient's permission for a different study provider to contact him/her, or provide contact information of a different study provider whom the patient can contact if interested.

Preliminary eligibility will be determined based on study staff interviews of interested subjects over the phone. Eligible subjects will then be scheduled for a screening visit.

Informed Consent

Written informed consent will be obtained by a licensed physician investigator prior to screening evaluation and testing. Subjects will be informed that they may withdraw from participation in the study at any point.

V. Study Procedures

The study will be conducted over 2 years, with subject recruitment complete after 18 months. Each eligible subject will participate in the study for 24 weeks. Following the screening visit, eligible subjects will return to the Massachusetts General Hospital Clinical Research Center (CRC) for as shown in the schema. Subjects in the Norditropin group will have 7 additional visits, and subjects in the No Treatment group will have 3 additional visits. Subjects who discontinue treatment for any reason will be asked to continue to return for study visits per their original randomization assignment.

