Patients will arrive after an 8-hour fast. For females, urine pregnancy test will be performed prior to the start of any procedures. When possible, women with regular menses will be studied within 10 days of the onset of the menstrual cycle.

1. Within one week prior to the baseline visit, subjects will come in the fasting state for a clonidine/arginine stimulation test to assess GH secretion (see methods).
2. Interval history and physical exam
3. Indirect calorimetry in the fasting state for the first 10 randomized subjects only
4. Fasting blood sample for glucose, insulin, IGF-1, AST, ALT, GGT, lipid panel, CRP, adiponectin, CK18
5. Standard 75g oral glucose tolerance test
6. DXA for quantification of total and regional fat and lean mass, VAT and SAT
7. Anthropometrics including height, weight, waist and hip circumferences, neck, mid-arm, and mid-thigh circumferences
8. Analysis of 24-hour food recall for macro- and micronutrient composition
9. Assessment of physical activity and lifestyle habits (including alcohol consumption) using questions from the 2013 Standard High School Youth Risk Behavior Survey (YRBS)
10. Instruction on reconstituting and administering Norditropin for subjects randomized to rhGH, with first injection prior to discharge

Safety Visits (2, 4, 6, and 18 weeks, Norditropin subjects only): **(1)** Interval H&P and safety assessment; **(2)** IGF-1, fasting glucose **(3)** Collection of used study drug and dispensation of new supply.

12 Week Visit: **(1)** Interval H&P and safety assessment; **(2)** IGF-1, fasting glucose **(3)** Collection of used study drug and dispensation of new supply for Norditropin subjects; **(4)** AST and ALT.

24 Week Visit: Subjects receiving treatment will be instructed to take their final Norditropin injection the night before the visit. Girls with regular menses will be studied within 10 days of the onset of the menstrual cycle. This visit will be identical to baseline with the addition of ¹H-MRS/MRI in the fasting state prior to OGTT. (clonidine/arginine stimulation test will *not* be repeated.) Indirect calorimetry will be performed only for the first 10 randomized subjects.

VI. Methods

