The risks to subjects will be minimized by using procedures which are consistent with sound research design. Subjects will be carefully screened to minimize potential risk of study procedures and treatments. A pregnancy test will be performed at each visit for female subjects of childbearing potential, and patients who become pregnant will be asked to discontinue participation in the study. Most importantly, the safety of subjects will be monitored closely by the principal investigator, co-investigators and DSMB, and subjects will be discontinued from the study if the risk to the subject is felt to be excessive.

Data and Safety Monitoring Plan

An independent data and safety monitoring board will be established to review safety data and adverse events. The DSMB will include a statistician, a gastroenterologist, and a pediatric endocrinologist, and will meet every 6 months. The studies will also be monitored continuously by the principal investigator ([name]).

Subjects will be instructed to report any adverse events immediately. A physician or nurse practitioner will be available on-call 24 hours/day, 7 days/week, to all study participants for any questions or concerns.

Clinical Trials Registration

The trial will be registered on clinicaltrials.gov, with [name] serving as the responsible party for registration and reporting of results.

XII. Dissemination of Results

Upon completion of the protocol, an abstract summarizing the primary results will be submitted to an appropriate national meeting (e.g., Pediatric Academic Societies or ENDO), and a manuscript comprehensively reporting the results will be submitted to an appropriate journal (e.g., *Journal of Clinical Endocrinology and Metabolism*). Preparation and submission of the primary manuscript reporting results is anticipated to be complete within 4 months of the last study visit for the last patient.

XIII. References Cited

1. [name] TL, Levitsky LL, Grinspoon SK, [name] M. Effect of body mass index on peak growth hormone response to provocative testing in children with short stature. *J Clin Endocrinol Metab.* 2009 Dec;94(12):4875-81.

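### Norditropin subjects have six scheduled post-baseline assessments and controls two, so by-arm adverse-event counts are expected to favour no treatment even if the drug does nothing

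*Combined protocol and SAP*

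**What the plan says.** Section V gives the visit totals after screening: "Subjects in the Norditropin group will have 7 additional visits, and subjects in the No Treatment group will have 3 additional visits". The Safety Visits entry in the same section accounts for the difference. Those visits are for "2, 4, 6, and 18 weeks, Norditropin subjects only", and each includes "Interval H&P and safety assessment" together with IGF-1 and fasting glucose. The 12 Week Visit has the same assessment and a fasting glucose, for both arms. Of the 24 Week Visit the plan says "This visit will be identical to baseline with the addition of" the MR scan; the baseline items carried forward include "Interval history and physical exam" and a fasting glucose, but no separately named safety assessment.

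Follow-up time is equal: "Each eligible subject will participate in the study for 24 weeks". Subjects who stop treatment "will be asked to continue to return for study visits per their original randomization assignment", so the unequal schedule continues after discontinuation.

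Section IX defines an adverse event broadly. It includes abnormal laboratory and exam findings and does not depend on relatedness. The Data and Safety Monitoring Plan in Section XI states: "An independent data and safety monitoring board will be established to review safety data and adverse events". It also tells all subjects to report adverse events at once and gives all of them on-call access. Section VII contains no adverse-event analysis by arm. No remote contact with controls is scheduled at weeks 2, 4, 6 or 18.

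**The concern.** Under this definition, the number of events recorded depends partly on how often someone asks, examines or draws blood. The symptoms named as possible rhGH effects (headache, edema, myalgia, arthralgia) are non-specific, and the control arm is the trial's only concurrent reference for their background rate. Controls go 12 weeks between scheduled questions. Norditropin subjects go two weeks at first and six weeks later.

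The trial has no placebo and no blinding, so nothing else in the design offsets the difference. At stake is how the safety data are read. A modest excess on Norditropin could come from the drug, from the visit schedule, or from both, and the data as collected could not separate them. This matters because Section I says the pilot is meant to inform later pediatric studies.

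**Working it through.** **1. Reproduce the plan's visit count.** From the visit descriptions in Section V:
- Norditropin: baseline + weeks 2, 4, 6, 12, 18, 24 = 7.
- No treatment: baseline + weeks 12, 24 = 3.

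This matches the stated 7 and 3. Without baseline the count is 6 v 2, a ratio of 3.0.

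**2. Expected ratio of recorded symptoms with no drug effect.** This model is an assumption and is not in the documents. True event rates are equal and constant over 24 weeks. A transient event is recorded if it is self-reported (probability s, the same in both arms) or if it falls within R weeks before a scheduled visit.

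Coverage C = sum over visits of min(R, weeks since the previous visit) / 24. The intervals are 2, 2, 2, 6, 6, 6 on Norditropin and 12, 12 on no treatment. Share recorded = s + (1 − s) × C.

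| R (weeks) | Weeks covered, Norditropin v control | Ratio, s = 0 | Ratio, s = 0.5 | Ratio, s = 0.8 |
|---|---|---|---|---|
| 2 | 12 v 4 | 3.00 | 0.750/0.583 = 1.29 | 0.900/0.833 = 1.08 |
| 4 | 18 v 8 | 2.25 | 0.875/0.667 = 1.31 | 0.950/0.867 = 1.10 |
| 6 | 24 v 12 | 2.00 | 1.000/0.750 = 1.33 | 1.000/0.900 = 1.11 |
| 12 | 24 v 24 | 1.00 | 1.00 | 1.00 |

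The ratio is 1.0 only if self-reporting is complete (s = 1) or recall spans the full 12 weeks.

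**3. Compare with chance.** Take 12 subjects per arm, one true event each, R = 4 and s = 0.5. Expected counts are 12 × 0.875 = 10.5 and 12 × 0.667 = 8.0, a gap of 2.5 events. If counts are roughly Poisson, the standard deviation of the difference is √(10.5 + 8.0) = 4.3. In this example the bias is smaller than chance variation.

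**4. Laboratory findings.** An abnormal fasting glucose can be found only when blood is drawn, so self-reporting does not help. Assume the same chance p of an abnormal value per draw in both arms, with independent draws. The chance of at least one flag is 1 − (1 − p)^k, where k is the number of draws:
- p = 2%: 11.4% (k = 6) v 4.0% (k = 2).
- p = 5%: 26.5% (k = 6) v 9.8% (k = 2).

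The Safety Visits entry gives six post-baseline draws on Norditropin. The rhGH risk text lists fasting glucose at weeks 2, 4, 6 and 12 and omits week 18. If week 18 were not drawn, k would be 5 and the Norditropin figures would be 1 − 0.98^5 = 9.6% and 1 − 0.95^5 = 22.6%. The direction is unchanged. Similarly, the Alternative Treatments text lists AST and ALT at weeks 6 and 18, which the Safety Visits entry does not. If they are drawn then, only Norditropin subjects attend. These passages must be reconciled.

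**The case against.** The strongest reply is that the plan already has an equalising provision: every subject is told to report adverse events at once. It deserves real weight. A reader who looks only at the 6 v 2 count might infer that a null drug would show a two- to three-fold excess, but that figure requires no self-reporting at all, and the documents give no ground for assuming so. With half of events self-reported the ratio is about 1.3. The provision reduces the bias but does not remove it: mild symptoms must still be volunteered, and laboratory and exam findings appear only at visits.

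Second, Section VII plans no by-arm adverse-event comparison, and the study-level stopping and halting rules count events in the GH group only. That stands, so a reader should not infer that the stopping rules or any planned test are compromised. The point concerns tabulations made for the monitoring board, the registry or the manuscript.

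Three further inferences go too far:
- The request to call with possible side effects, placed in the rhGH risk text, adds little by arm, because Section XI gives all subjects an equivalent instruction.
- The documents describe no structured or scripted enquiry, and week 24 names only an interval history and exam. Two is therefore the generous count for controls.
- Extra ascertainment on the drug arm inflates apparent harm. It would not conceal a true excess, although it would make one harder to attribute.

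Finally, the additional Norditropin visits serve dose adjustment, glucose monitoring and drug supply. Nothing here argues against them.

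**Conclusion.** The imbalance is certain: six scheduled post-baseline assessments against two, confirmed by the plan's own totals. Its consequence holds in expectation. By-arm counts are expected to be higher on Norditropin with no drug effect, unless self-reporting is complete or recall lasts 12 weeks. The size cannot be settled from the documents. It ranges from about 1.1 (80% self-reported) through about 1.3 (half) to 2.0 to 3.0 (none), for recall of 2 to 6 weeks and equal true rates. At about 12 per arm it may be lost in chance variation. The primary endpoint, its power and the planned analyses are untouched. This is a modest flaw in the comparability of the safety data, worth correcting because correction is cheap.

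**What to change.** Write one short adverse-event script and use it in both arms. Put it to Norditropin subjects at their existing visits and to No Treatment subjects by telephone at weeks 2, 4, 6 and 18, and to both arms at weeks 12 and 24. Scheduled symptom enquiry then becomes 6 v 6, and the expected ratio under the model above is 1.0.

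Telephone calls cannot reveal laboratory or exam findings. In addition, or at minimum if the calls are not adopted, state in Section VII that any by-arm comparison of those findings uses only the shared week 12 and week 24 visits (2 v 2). List events found only at the Norditropin-only visits separately, and do not present them as a comparison.

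The cost is 4 × 12 = 48 short calls by existing staff, slightly more contact with controls, and fewer events in the comparative table. If symptoms were compared only through a fixed-recall question at the shared visits, early events would be missed. With a four-week recall, for example, the comparison would cover 8 of 24 weeks and none of weeks 0 to 8, which is why the calls are preferable for symptoms. Neither step changes dosing, stopping rules or the primary analysis. Reporting bias from knowledge of the assigned arm would remain and should be stated as a limitation.

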For all female subjects, urine pregnancy tests will be performed at all visits, and a positive pregnancy test will result in immediate discontinuation. At baseline, 12 weeks, and 24 weeks, subjects will be counseled regarding lifestyle modification (see Methods). Subjects will continue to receive care from their regular medical providers, including hepatologists, throughout the study. Any subject not under the care of a hepatologist who is found at screen to have $\geq 5\%$ liver fat and significantly elevated AST or ALT will be offered referral to the hepatology clinic.

Screen: (1) Informed consent; (2) Detailed H&P, including medications and alcohol habits; (3) blood sampling for IGF-1, CBC, HbA1c, fasting glucose, AST, ALT, total bilirubin, Hepatitis B sAg, Hepatitis C antibody; (4) ^1H -MRS/MRI of abdomen in fasting state for quantification of liver fat. (This scan will also be used to assess VAT and SAT for those eligible subjects participating in the baseline visit.)

Randomization and Study Drug: After the screening visit, eligible patients who wish to participate will be randomized in a 1:1 ratio to Norditropin vs. no treatment. The study will not be blinded and placebo will not be used to avoid daily injections without benefit for subjects randomized to no treatment. Randomization will be stratified by gender and Vitamin E use. The starting dose of Norditropin will be 0.5 mg daily, which is a recommended dose for restarting growth hormone in young adults with GHD during the transition from adolescence to adulthood (70). IGF-1 will be checked at 2, 4, 6, 12, and 18 weeks, and will be reviewed by the PI. Active dose adjustments will be performed per algorithm as follows. A 20% dose increase will be performed for any Norditropin subject with IGF-1 SDS ≤ 0 . Conversely, a 20% decrease in dose will be performed for any Norditropin subject with IGF-1 SDS > 2 .

| Norditropin Dosing Algorithm (starting dose 0.5 mg) | | |
|--|-------------------------------|---------------------|
| IGF-1 SDS ≤ 0 | $0 < \text{IGF-1 SDS} \leq 2$ | IGF-1 SDS > 2 |
| 20% dose increase | maintain dose | 20% dose reduction* |
| *Subjects with persistent IGF-1 SDS > 2 after 2 dose reductions will be discontinued from the study. | | |

Baseline Visit:

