Lifestyle Counseling: Subjects will receive lifestyle counseling from study MDs or nutritionists at the baseline, 12 week, and 24 week visits, with recommendations and resources provided based on the 2010 Dietary Guidelines for Americans (http://www.cnpp.usda.gov/sites/default/files/dietary_guidelines_for_americans/PolicyDoc.pdf) and the 2008 Physical Activity Guidelines for Americans (<http://health.gov/paguidelines/guidelines/summary.aspx>). Emphasis will be placed on physical activity (150+ minutes weekly); reduction of saturated fats, total fats, and sugary beverages; and increased consumption of fruits and whole grains.

VII. Biostatistical Analysis

Statistical Consideration – Data Interpretation: The primary endpoint will be change in hepatic fat as measured by ¹H-MRS after 24 weeks of randomized treatment. Secondary endpoints will include changes in ALT, AST, GGT, VAT, CRP, adiponectin, IGF-1, lipids, fasting and 2-hour glucose and insulin, HbA1c, and respiratory quotient measured by indirect calorimetry. Permuted block randomization will be performed, stratified by gender and use of Vitamin E.

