Analysis will be intention-to-treat, using all available data from all subjects. Wilk-Shapiro test will be used to assess for normality of distribution of all variables, and variables that are not normally distributed will be appropriately transformed. Baseline variables will be compared between treatment groups, and any baseline variable that is statistically different between treatment groups will be adjusted for in subsequent analysis. Changes in variables measured only at baseline and 6 months, including the primary endpoint of liver fat, will be initially assessed using a two-sample t-test comparing mean changes between treatment groups. A critical alpha level of 0.05 will be used as the threshold for significance, and all statistical tests will be two-tailed. Subsequently, adjusted analyses will be performed including as covariates any baseline characteristics that differ between treatment groups and any differential changes in nutritional intake or physical activity between treatment groups over the study duration. For variables measured at ≥ 3 timepoints throughout the study (e.g., IGF-1, AST and ALT), we will analyze the longitudinal data using general linear mixed effects modeling, testing for time x treatment group interaction. The primary analysis will be an intention to treat analysis using all available data. We will consider secondary multiple imputation based analyses if necessary.

A supplementary analysis will be performed assessing stimulated growth hormone levels in response to Arginine testing. Using peak GH as the independent variable, we will assess the hypothesis that peak GH will be negatively associated with liver fat quantity.

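### Change in HbA1c is a secondary endpoint, but the written visit lists name HbA1c only at screening; check the schema and reconcile the text

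*Combined protocol and SAP*

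**What the plan says.** **Endpoint.** Section VII (Biostatistical Analysis) defines the secondary endpoints as changes, and the list closes with "fasting and 2-hour glucose and insulin, HbA1c, and respiratory quotient measured by indirect calorimetry".

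**Screening.** Section V, Screen, calls for "blood sampling for IGF-1, CBC, HbA1c, fasting glucose, AST, ALT, total bilirubin, Hepatitis B sAg, Hepatitis C antibody". HbA1c also appears among the exclusion criteria in section III, which explains the screening draw.

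**Later visits.** Section V states: "Subjects in the Norditropin group will have 7 additional visits, and subjects in the No Treatment group will have 3 additional visits". It says that these visits proceed "as shown in the schema"; the figure itself is not visible. The baseline blood list reads "Fasting blood sample for glucose, insulin, IGF-1, AST, ALT, GGT, lipid panel, CRP, adiponectin, CK18". The 24-week visit is defined by reference to it: "This visit will be identical to baseline with the addition of" MRS/MRI.

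**Analysis.** For "Changes in variables measured only at baseline and 6 months", section VII prescribes a two-sample t-test of mean changes. For variables with three or more time points it prescribes a mixed-effects model with a time-by-treatment interaction.

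**The concern.** An endpoint defined as a change needs a value before treatment and a value after it. The written schedule delivers the first and not the second. Staff who work from the visit text would have no instruction to request HbA1c after screening in either arm, and a result that was never obtained cannot be recovered at analysis. At stake is one prespecified glycaemic outcome in an open-label trial whose second aim concerns glucose homeostasis.

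**Working it through.** **1. Reproduce the visit counts.** Counting the visits described in section V:

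- Norditropin: baseline (1) + weeks 2, 4, 6, 18 (4) + week 12 (1) + week 24 (1) = 7
- No treatment: baseline (1) + week 12 (1) + week 24 (1) = 3

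Both agree with the plan's own figures, so no written visit has been overlooked.

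**2. Look for HbA1c at each visit.**

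| Visit | Arm | Blood tests named in the visit text | HbA1c |
|---|---|---|---|
| Screening | all | IGF-1, CBC, HbA1c, glucose, AST, ALT, bilirubin, hepatitis serology | yes |
| Baseline | both | the fasting list quoted above, plus OGTT | no |
| Weeks 2, 4, 6, 18 | Norditropin | IGF-1, glucose | no |
| Week 12 | both | IGF-1, glucose, AST, ALT | no |
| Week 24 | both | as baseline | no |

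HbA1c is therefore named at 0 of 7 post-screening visits on Norditropin and 0 of 3 on no treatment. After baseline the counts are 0 of 6 and 0 of 2. Values per subject: 1 listed, 2 needed.

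**3. Look for HbA1c in the rest of the text.** It appears in three places in all: the exclusion criterion, the screening labs and the endpoint list. The OGTT description in section VI samples only insulin and glucose. The blood volumes in section VIII (99 cc at baseline and at week 24; 5 or 8 cc at the visits between) are not broken down by assay, so they neither include nor exclude HbA1c.

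**4. Is the gap general or isolated?** Every other secondary endpoint in section VII has at least one measurement after baseline:

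- ALT and AST: weeks 12 and 24
- IGF-1 and fasting glucose: weeks 12 and 24 in both arms, plus weeks 2, 4, 6 and 18 on Norditropin
- GGT, CRP, adiponectin and lipids: week 24
- Insulin (fasting and two-hour) and two-hour glucose: week 24 fasting sample and OGTT
- VAT: week 24 MRI
- Respiratory quotient: week 24, first 10 randomised subjects only

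HbA1c is the only one with none.

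**5. Does the gap touch the stated power?** Section VII allows for 20% discontinuation: 24 × 0.80 = 19.2, so 19 evaluable, taken here as 9 and 10. For a two-sided t-test at 0.05 and a difference of 1.4 SD, the noncentrality is 1.4 × √(9 × 10 / 19) = 3.05 on 17 degrees of freedom. This gives 81.9% power, and 80% is reached at 1.37 SD. The plan's figure of about 1.4 SD for secondary variables reproduces, and the timing of HbA1c does not enter it.

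**The case against.** **The schema may supply it.** The visits are said to follow a schema that cannot be seen, and what is not visible cannot be called missing. This stands. It makes the consequence conditional, though not the observation about the written lists. If the schema does show a later HbA1c, section V still needs to agree with it, because week 24 is defined through an itemised list without HbA1c.

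**The visit lists are not exhaustive.** They omit pregnancy tests at the safety and 12-week visits, lifestyle counselling, and AST and ALT at weeks 6 and 18. Naming HbA1c as an endpoint itself signals an intention to repeat it, so one word dropped from a lab list is a plausible explanation. This stands in part. Each of those other items is supplied elsewhere: in the opening paragraphs of section V, under Lifestyle Counseling in section VI, and under Alternative Treatments. No visible section does the same for HbA1c.

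**A reader might infer that the screening value is the baseline and the t-test the right analysis.** The documents do not settle this. The dual use of a screening measurement is written down only for the scan: "This scan will also be used to assess VAT and SAT for those eligible subjects participating in the baseline visit". For blood tests the pattern is the opposite, since IGF-1, fasting glucose, AST and ALT are drawn at screening and again at baseline. The schema might also show a baseline HbA1c, or three or more time points, and section VII would then call for the mixed model.

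**Conclusion.** The inconsistency holds for the written text: a stated secondary endpoint is not delivered by the stated visits. Unless the schema lists HbA1c after screening, following the text yields one value per subject and none after randomisation in either arm, and the change cannot be computed.

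Two stronger readings are not supported. One is that the trial will certainly lack a follow-up HbA1c; the unseen schema prevents that conclusion. The other is that the assessment of glucose homeostasis fails. HbA1c is not among the measures in Aim 2a or in the stopping rules, and fasting glucose is listed at baseline, week 12 and week 24 in both arms. The primary endpoint and the power statement are also untouched.

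Severity is minor: one secondary endpoint in a 24-subject pilot.

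**What to change.** Check the schema against the text first.

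- **If the schema lists HbA1c after screening:** bring the visit lists in section V into line with it, keeping its time points and its source for the baseline value.
- **If it does not,** choose one of two options, in both arms and on existing draws:
  - Add HbA1c to the baseline fasting sample. Week 24 inherits it. Cost: up to 24 × 2 = 48 assays.
  - Add HbA1c at week 24 only, and state that the screening value is its baseline. Cost: up to 24 × 1 = 24 assays.

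Then apply the section VII rule that fits the number of time points: the t-test of changes if there are only baseline and week 24, the mixed model if there are three or more.

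Neither option adds a visit; each needs only a short text amendment. Subjects already past week 24 when the text is amended could not be recovered by a new assay. The documents do not give enrolment status, so the number affected, if any, is unknown.

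### The adjusted liver-fat analysis lets chance baseline differences and on-study lifestyle changes choose its covariates, leaves baseline liver fat out of the fixed model, and no sentence says which analysis is decisive

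*Combined protocol and SAP*

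**What the plan says.** All the analysis text is in section VII, Biostatistical Analysis, under Statistical Consideration – Data Interpretation.

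- **Baseline rule.** Baseline variables are compared between arms, and "any baseline variable that is statistically different between treatment groups will be adjusted for in subsequent analysis". A later sentence repeats the rule for characteristics that differ, without the word statistically.
- **First test.** Variables measured only at baseline and six months, "including the primary endpoint of liver fat, will be initially assessed using a two-sample t-test comparing mean changes between treatment groups".
- **Adjusted analyses.** These follow the t-test. Besides the baseline characteristics that differ, they include "any differential changes in nutritional intake or physical activity between treatment groups over the study duration". No test or threshold is given for calling such a change differential.
- **What is called primary.** "The primary analysis will be an intention to treat analysis using all available data". This names a population and a data set, not a test or a model.

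Baseline liver fat is not named as a covariate. Neither is gender or Vitamin E use, although randomisation is stratified by both. Every randomised subject has a baseline value, because the screening visit in section V includes "MRI of abdomen in fasting state for quantification of liver fat". Section V also states that the trial is unblinded and has no placebo.

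**The concern.** In a randomised trial any baseline difference between arms is chance. A between-arm significance test therefore says nothing about whether a variable predicts the outcome, which is what makes a covariate useful. The rule lets chance decide which terms enter the adjusted model. It usually leaves out baseline liver fat, the obvious candidate.

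The diet and activity terms are a different problem. They are measured after randomisation, and subjects know their assignment. If treatment, or knowledge of it, alters diet or activity and that alters liver fat, adjustment may remove part of the effect that an intention-to-treat comparison should capture.

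Two things are at stake: precision with about 19 evaluable subjects, and knowing in advance which model will be reported. If the t-test and the adjusted model disagree, the plan does not say which governs.

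**Working it through.** **Inputs from the documents.** Effect 4.2 points, SD 3.1, 24 randomised, 19 evaluable (Sample Size and Power Calculations); two-sided 0.05 (Data Interpretation); 1:1 allocation (section V).

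**Assumed.** A 10 v 9 split; 3.1 is the SD of change (the plan calls it only a published SD); the baseline/week-24 correlation ρ, which the documents do not give; equal variances at the two times; gender 5/5 v 5/4; two Vitamin E users per arm.

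**1. The plan's own power.** Noncentrality = (4.2/3.1) × √(10×9/19) = 1.355 × 2.176 = 2.949. With 17 df the critical value is 2.110 and power is 79.4%. The stated 80% is that of the unadjusted t-test.

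**2. How many variables the rule can reach.** Section V, Baseline Visit:
- "Fasting blood sample for glucose, insulin, IGF-1, AST, ALT, GGT, lipid panel, CRP, adiponectin, CK18": 10, with the lipid panel as one.
- Two-hour glucose and insulin from the glucose tolerance test: 2.
- "DXA for quantification of total and regional fat and lean mass, VAT and SAT": 5.
- "Anthropometrics including height, weight, waist and hip circumferences, neck, mid-arm, and mid-thigh circumferences": 7.

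The total is 10 + 2 + 5 + 7 = 24, or 25 with screening liver fat. HbA1c, peak GH, MRI fat depots, and diet and activity items are not counted.

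**3. How often the rule fires.** For k independent variables the chance that at least one is flagged is 1 − 0.95^k: 23% for 5, 40% for 10, 72% for 25. Any one variable, including liver fat, is flagged in about 5% of trials. To be flagged, observed means must differ by about 2.110 × √(1/10 + 1/9) = 0.97 SD.

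**4. Power of the selected model (simulated).** Flagged variables are added to the change-score model; the t-test comparator is 79%.

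| Assumption about baseline variables | 5 | 10 | 25 |
|---|---|---|---|
| Independent; all but liver fat unrelated to change (ρ = 0.5) | 77% | 73% | 63% |
| Mutually correlated at 0.5; jointly explain 25–50% of change | 78–81% | 76–81% | 73–77% |

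**5. Type I error.** The t-test holds 5%, and the selected model alone holds 5% or less. If either result could be claimed, the rate is 5.5%, 6.2% and 7.0% for 5, 10 and 25 independent variables. It reaches about 8.6% with 25 correlated variables that predict change, hence a range of roughly 5.5–9%.

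**6. A fixed ANCOVA instead.** The correlation of baseline with change has size r = √((1−ρ)/2), so the residual SD is 3.1 × √(1−r²) = 3.1 × √((1+ρ)/2). Simulated power, allowing for lost degrees of freedom and chance imbalance, with baseline liver fat and gender in the model:

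| ρ | 0.3 | 0.5 | 0.7 | 0.85 | 0.95 |
|---|---|---|---|---|---|
| Residual SD before gender | 2.50 | 2.68 | 2.86 | 2.98 | 3.06 |
| Power | 91% | 87% | 82% | 79% | 77% |

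Break-even with the t-test is near ρ = 0.85. If baseline is unrelated to change, power is 75.8%, or 75.2% with Vitamin E as well.

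**7. The other reading of 3.1.** If it is the SD of a single liver-fat value, the SD of change is 3.1 × √(2(1−ρ)) = 3.67, 3.10, 2.40 and 1.70 at ρ = 0.3, 0.5, 0.7 and 0.85. The t-test then has 65%, 79%, 95% and >99% power; ANCOVA has 80%, 87%, 96% and >99%.

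**8. Diet and activity.** The documents give no basis for the size of any on-study shift or its effect on liver fat, so this part is not quantified.

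**The case against.** The strongest reply is that the lead analysis can be recovered from the text. The t-test comes first, the alpha sentence follows it directly, the adjusted analyses come afterwards, and the power statement is that of the t-test. Nothing allows an adjusted result to replace it. The study is described as a pilot, and asking whether lifestyle explains a difference is reasonable when both arms are counselled. Naming the t-test as decisive would settle multiplicity with one sentence.

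Much of this stands, and it rules out several stronger conclusions that a reader might draw:

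- **That the primary test is invalid or the 80% power wrong.** The t-test is valid and the figure reproduces.
- **That type I error is inflated as planned.** This needs a rule that either result may be claimed, and the plan has none.
- **That the rule costs 16 points of power (79% to 63%).** That figure assumes 25 independent variables, all but liver fat unrelated to change. The listed measures overlap heavily, and the background section links visceral fat to fatty liver. Under the correlated, predictive assumptions the loss with 25 variables is about 2 to 6 points, and with 5 or 10 it largely disappears.
- **That the t-test fails when an imbalance goes unflagged.** In the 23% of trials where baseline liver fat differs by more than 0.5 SD but is not flagged, its type I error is 7.8% at ρ = 0.5. That is a subset picked for its imbalance; over all trials the rate is 5%.
- **That lifestyle adjustment biases the result by a known amount.** The documents support only that it may change what is estimated.

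What the reply does not answer is that the adjusted analysis is still planned, its covariates are unknown until the data are seen, and the one baseline measure collected on everyone for this endpoint enters only by chance. Naming the t-test would settle which result governs, but not this.

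**Conclusion.** The point holds as an improvement in method. The adjusted analysis selects baseline covariates by chance, includes baseline liver fat in about 5% of trials, and adds post-randomisation terms that may move it away from the total intention-to-treat effect. No sentence designates the decisive test, although the t-test appears to be intended.

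The size is moderate and depends on assumptions. The selected model has about 63% to 81% power against 79% for the t-test, depending on the number of baseline variables, their correlation and how well they predict change. A fixed ANCOVA gains about 12 points at ρ = 0.3, about 8 at 0.5 and about 3 at 0.7, is level near 0.85, and loses about 3 at 0.95. These figures take 3.1 as the SD of change, and ρ is assumed throughout. The case for prespecification does not depend on ρ; the power gain does.

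**What to change.** In section VII:

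1. Name one decisive analysis: an ANCOVA of week-24 liver fat (or its change) on treatment, with baseline liver fat and gender as fixed covariates. State in advance whether Vitamin E use is included.
2. Delete the rule that selects baseline covariates by between-arm differences, in both places where it appears.
3. Label any analysis adjusted for on-study diet or activity changes as exploratory.
4. Keep the unadjusted t-test as supportive.

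**Cost.** Wording only, with no new data. The model uses two degrees of freedom beyond the t-test, or three with Vitamin E. Gender costs 0.4 to 0.8 point of power if it does not predict change, and Vitamin E a further 0.4 to 0.7 point. At ρ = 0.95 the loss is 79.4 − 76.6 = 2.8 points. At worst, with baseline unrelated to change, it is 79.4 − 75.8 = 3.6 points, or 79.4 − 75.2 = 4.2 with Vitamin E included.
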